8.4. Adverse Events (AEs) Serious Adverse Events (SAEs), and Other Safety Reporting

The definitions of adverse events (AEs) and serious adverse events (SAEs) can be found in Appendix 3.

The investigator and any qualified designees are responsible for detecting, documenting, and recording events that meet the definition of an AE or SAE and remain responsible for following up AEs that are serious, considered related to the study intervention or study procedures, or that caused the participant to discontinue the study intervention. This includes events reported by the participant (or, when appropriate, by a caregiver, surrogate, or the participant's legally authorized representative).

The method of recording, evaluating, and assessing causality of AEs and SAEs and the procedures for completing and transmitting SAE reports are provided in Appendix 3.

8.4.1. Time Period and Frequency for Collecting AE and SAE Information

All SAEs will be collected from the signing of the informed consent form until the scheduled 30month visit (after entering the MERINO trial). Medical occurrences that begin before the start of study intervention but after obtaining informed consent will be recorded as medical history/current medical conditions, not as AEs.

All SAEs will be recorded and reported to the sponsor or designee immediately and under no circumstance should this exceed 24 hours, as indicated in Appendix 3. The investigator will submit any updated SAE data to the sponsor within 24 hours of it being available.

Investigators are not obligated to actively seek information on AEs or SAEs after conclusion of the study participation. However, if the investigator learns of any SAE, including a death, at any time after a participant has been discharged from the study, and the investigator considers the event to be reasonably related to the study intervention or study participation, the investigator must promptly notify the sponsor.

8.4.2. Method of Detecting AEs and SAEs

Care will be taken not to introduce bias when detecting AEs and/or SAEs. Open-ended and nonleading verbal questioning of the participant is the preferred method to inquire about AE occurrences.

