1.3. Schedule of Activities (SoA)

| | | | | MERI | NO | | | | MER | INO:2 |
|---|--------|-----------------|------------|------------|-------------|-----------------|-------------|-----------------|--------------------------|---------------|
| Overview of the data collection | Screen | M00 | M01 | M02 | M03 | M06 | M09 | M12 | M12- M30 | M30 |
| Weeks | (-4)–0 | 1 | 5 +/- 1 | 9 +/- 1 | 13 +/- 2 | 26 +/- 2 | 39 +/- 2 | 52 +/- 2 | 52- 130 ⁹⁾ | 130 +/- 10 |
| Study information, eligibility ¹⁾ , and informed consent | Х | | | | | | | | X | |
| Regular visit | | Х | Х | | Х | Х | Х | Х | | |
| Safety monitoring | | | Х | Х | Х | Х | Х | Х | X | |
| First dose | | Х | | | | | | | | |
| Medical drug extradition to patient | | Х | | | | Х | | | X | |
| Medical drug counting | | | | | | Х | | Х | | Х |
| Person characteristics | | | | | | | | | | |
| Demographic and medical history 1) | | Х | | | | | | | | |
| Concomitant medication | Х | Х | Х | | Х | Х | Х | Х | | Х |
| Safety and laboratory assessments | | | | | 1 | | 1 | 1 | | |
| Laboratory sample for screening 2) | Х | | | | | | | | | |
| Laboratory safety monitoring | | | Х | Х | Х | Х | Х | Х | X ¹⁰⁾ | |
| Biobank samples | | X ³⁾ | | | | X ⁴⁾ | | X ⁴⁾ | | |
| Adverse events | | | Х | | Х | Х | Х | Х | X | |
| Serum hCG in fertile women | Х | Х | Х | Х | Х | Х | Х | Х | X | |
| Patient-reported outcome measures | | | | | | | | | | |
| Hand pain on most days (yes/no) | Х | | | | | | | | | |
| Hand pain previous 48 hours (VAS) | Х | Х | Х | | Х | Х | Х | Х | | Х |
| Pain in most painful joint previous 48 hours (VAS) | | Х | Х | | Х | Х | Х | Х | | Х |
| Hand diagram | | Х | | | | Х | | | | |
| OMERACT-OARSI responder criteria | | Х | Х | | Х | Х | Х | Х | | X |
| Australian/Canadian hand index (AUSCAN) | | Х | Х | | Х | Х | Х | Х | | Х |
| Heath-related quality of life (EQ-5D) | | Х | Х | | Х | Х | Х | Х | | X |
| Michigan Hand Outcomes questionnaire (MHOQ) | | Х | | | | Х | | | | |
| Hospital Anxiety and Depression scale (HADS) | | Х | | | | Х | | | | |
| Pain Catastrophizing Scale (PCS) | | Х | | | | Х | | | | |
| Pain Sensitivity Questionnaire (PSQ) | | Х | | | | Х | | | | |
| Knee injury and Osteoarthritis Outcome Score (KOOS)-12 | | Х | | | | Х | | | | |
| Hip disability and Osteoarthritis Outcome Score (HOOS)-12 | | Х | | | | Х | | | | |
| Physical examination | | | | | | | | | | |

| ACR criteria for hand, hip and knee OA | Х | | | | | | | |
|---|-----------------|---|---|---|---|---|---|---|

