| Tender and swollen joint count | | Х | Х | Х | Х | Х | Х | |
| Anthropometric and cardiovascular assessment 5) | | Х | Х | Х | Х | Х | Х | |
| Grip strength | | Х | | | Х | | Х | |
| Pain sensitization 6) | | Х | | | Х | | | |
| Imaging outcome measures | | | | | | | | |
| Chest radiograph | Х | | | | | | | |
| Conventional hand radiographs | Х | | | | Х | | Х | X |
| Ultrasound of fingers | X ⁷⁾ | Х | Х | Х | Х | Х | Х | |
| Ultrasound of hips and knees | Х | | | | Х | | | |
| MRI | | Х | | | Х | | | |
| Knee OA sub-study ⁸⁾ | | | | | | | | |
| Synovial needle biopsy of one knee | | Х | | | Х | | | |
| Knee pain previous 48 hours (VAS) | | Х | | | Х | | | |

VAS = visual analogue scale; OMERACT-OARSI = Outcome Measures in Rheumatology Osteoarthritis Research Society International; EQ-5D = EuroQol 5 dimensions; MRI = Magnetic Resonance Imaging.

- 1. Birth date, sex, ethnic origin, marital and work status, exercise, smoking, alcohol, hormonal factors (women), previous joint-related therapies, and comorbidities.
- 2. Hemoglobin, white blood cells with differentials, platelet counts, ASAT, ALAT, albumin, creatinine, GFR, CRP, ESR, IGRA, HIV, Hepatitis B and C.
- 3. Plasma, serum and full blood.
- 4. Plasma and serum.
- 5. Including pulse rate, systolic and diastolic blood pressure and body weight will be assessed at all visits. Height will be measured at baseline only.
- 6. Includes Pressure Pain Thresholds (PPT), CPM = Conditioned Pain Modulation and temporal summation.
- 7. Confirm two interphalangeal joints with a positive power Doppler signal of at least grade 1 or B mode grey scale synovitis of at least grade 2 on ultrasound.
- 8. Sixteen volunteers with concomitant knee OA.
- 9. Follow-up in the outpatient clinic as agreed between participant and treating physician.
- 10. Safety monitoring according to National recommendations in Norway for DMARD treatment.

2. Introduction

The MERINO:2 study is an extension of the ongoing MERINO trial. This trial involves participants with erosive hand OA receiving either MTX or placebo. The MERINO:2 plans for an extended observational period of the MERINO trial, 30 months after starting the original study. Some of these participants have expressed a desire to receive MTX open-label after the MERINO trial and are followed as ordinary in an outpatient clinic. The study aims to provide unique data on the long-term effects of sustained MTX treatment, particularly on structural joint damage.

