8.3. Safety Assessments

All participants will be monitored according to the National procedure for diagnosis, treatment and follow-up of rheumatoid arthritis in Norway (30), chapter 10.1. Blood tests recommended for monitoring: Hemoglobin, red blood cells, white blood cells with diff. Counts, platelets, ALT, creatinine, (SR and CRP). Patients with comorbidity, abnormal blood tests, and / or polypharmacy treated with DMARD may require more frequent laboratory tests than the general recommendations in the table.

| Drug | Monitoring interval based on duration of treatment | | |
|-------------|--|------------|-----------|
| | <3 months | 3-6 months | >6 months |
| Metotreksat | 2–4 weeks | 8–12 weeks | 12 weeks |

Table: Monitoring interval for blood testing in patients using DMARDs

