10.3.1. Definition of AE

AE Definition An AE is any untoward medical occurrence in a patient or clinical study participant, temporally associated with the use of study intervention, whether or not considered related to the study intervention.

• NOTE: An AE can therefore be any unfavorable and unintended sign (including an abnormal laboratory finding), symptom, or disease (new or exacerbated) temporally associated with the use of study intervention.

Definition of Unsolicited and Solicited AE

- An unsolicited AE is an AE that was not solicited using a participant diary and that is communicated by a participant who has signed the informed consent. Unsolicited AEs include serious and nonserious AEs.
- Potential unsolicited AEs may be medically attended (ie, symptoms or illnesses requiring a hospitalization, emergency room visit, or visit to/by a healthcare provider). The participants will be instructed to contact the site as soon as possible to report medically attended event(s), as well as any events that, though not medically attended, are of participant concern. Detailed information about reported unsolicited AEs will be collected by qualified site personnel and documented in the participant's records.
- Unsolicited AEs that are not medically attended nor perceived as a concern by the participant will be collected during an interview with the participants and by review of available medical records at the next visit.
- Solicited AEs are predefined events for which the participant is specifically questioned, and which are noted by the participant in their diary.

Events Meeting the AE Definition

- Any abnormal laboratory test results (hematology, clinical chemistry, or urinalysis) or other safety assessments (e.g., ECG, radiological scans, vital signs measurements), including those that worsen from baseline, considered clinically significant in the medical and scientific judgment of the investigator (i.e., not related to progression of underlying disease).
- Exacerbation of a chronic or intermittent pre-existing condition including either an increase in frequency and/or intensity of the condition.
- New conditions detected or diagnosed after study intervention administration even though it may have been
 present before the start of the study.
- Signs, symptoms, or the clinical sequelae of a suspected drug-drug interaction.

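### Adverse events have no common ascertainment schedule in MERINO:2 and no enquiry at month 30, so capture is likely to be denser in current MTX users

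*Protocol*

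**What the plan says.** Protocol 8.4.1 sets the window: "All SAEs will be collected from the signing of the informed consent form until the scheduled 30month visit". It makes no distinction by treatment group.

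Protocol 8.4.2 undertakes to avoid bias in finding events and then states the method: "Open-ended and nonleading verbal questioning of the participant is the preferred method to inquire about AE occurrences". Appendix 3 (10.3.1) adds two routes. Participants are told to contact the site about medically attended or worrying events, and other unsolicited events "will be collected during an interview with the participants and by review of available medical records at the next visit".

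In the Schedule of Activities (1.3), MERINO:2 has two columns, M12-M30 and M30. Note 9 describes the first: "Follow-up in the outpatient clinic as agreed between participant and treating physician". Note 10 covers the laboratory row in that column: "Safety monitoring according to National recommendations in Norway for DMARD treatment".

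Section 8.3 opens broadly: "All participants will be monitored according to the National procedure for diagnosis, treatment and follow-up of rheumatoid arthritis in Norway". Its interval table, however, is headed "Monitoring interval based on duration of treatment" and its caption limits it to patients using DMARDs.

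Section 9.2 plans safety analyses in participants exposed to the intervention, grouped by what they actually received.

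**The concern.** The detection method needs an occasion on which someone asks. For a participant on usual care, or one who has stopped MTX, the schedule names none between the end of MERINO and month 30, and none at month 30 itself. A participant on MTX has recurring safety contacts through blood monitoring, each of which is a chance for an event to be mentioned and recorded.

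If capture differs in this way, event rates by treatment received mix true risk with intensity of observation. Participants who took MTX in MERINO and then went to usual care belong to the exposed population of 9.2, as do those who stop after the three-month try-out described in 6.3. Events arising after they stop are the ones most likely to be missed. The event of special interest in 8.4.6, prolonged cough, is not asked about at month 30 either.

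**Working it through.** The protocol gives no figure to reproduce. The check sets the schedule against the text and then counts the contacts that the text implies.

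**Step 1: the schedule, row by row.** Each row checked has ten cells (Screen, M00, M01, M02, M03, M06, M09, M12, M12-M30, M30). The last two read:

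| Row | M12-M30 | M30 |
|---|---|---|
| Regular visit | blank | blank |
| Safety monitoring | marked | blank |
| Laboratory safety monitoring | marked (note 10) | blank |
| Adverse events | marked | blank |
| Concomitant medication | blank | marked |
| Hand pain (VAS) | blank | marked |

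The last two rows show that the empty month-30 cell for adverse events is not a column shift in the extracted table.

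**Step 2: what happens at month 30.** Section 2.1 describes electronic questionnaires and hand radiographs. Appendix 2 holds the forms: pain VAS with two analgesic-use questions, AUSCAN, EQ-5D-5L and a medication list. None asks about adverse events, hospital admissions or new diagnoses.

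**Step 3: what happens between M12 and M30.** Adverse events and safety monitoring are marked without a split by treatment, but note 9 leaves contact to agreement with the treating physician. The only fixed intervals are those in 8.3, and they are indexed by duration of treatment. M12 is week 52 and M30 is week 130, so the period is 130 − 52 = 78 weeks. Assuming that MTX is started or continued at M12 and kept to M30:

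- New starter, first 13 weeks at 2 to 4 week intervals: 13/4 to 13/2, about 3 to 6 tests.
- Next 13 weeks at 8 to 12 week intervals: 13/12 to 13/8, about 1 test.
- Last 52 weeks at 12-week intervals: 52/12, about 4 tests.
- Total for a new starter: 3 + 1 + 4 = 8 to 6 + 1 + 4 = 11.
- Continuing user at 12-week intervals: 78/12 = 6.5, about 6 tests.
- A starter who stops at three months: about 3 to 6 tests, then none specified for the remaining 78 − 13 = 65 weeks.
- Usual care throughout: none specified.

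These are blood tests, not event enquiries, and a blood test does not by itself reveal a hospital admission. They show only where recurring safety contact is written down.

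**Step 4: the collection window.** Under 8.4.1 it opens at signed consent. The Schedule of Activities places MERINO:2 consent anywhere in M12-M30, and 10.1.4 describes an SMS invitation with digital consent. For many participants the window will be shorter than 78 weeks, and the protocol does not say how events between M12 and consent are treated.

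**The case against.** Four counter-arguments deserve weight.

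- **Other routes exist.** Verbal questioning is the preferred method, not the sole one. Section 8.4 makes investigators and designees responsible for detecting events, Appendix 3 provides for self-report and record review, 2.1 mentions ordinary outpatient consultations, and 6.3 expects an evaluation about three months after MTX is tried. A reader might infer that spontaneous contact is the only route for participants off MTX. The text does not support that.
- **The schedule does not split by treatment.** Adverse events are marked in M12-M30 for everyone, and 8.3 literally covers all participants. A reader might infer that capture depends on being on MTX. The documents support only that it is likely to be unequal. Section 8.3 still gives an untreated participant no interval, so its opening sentence and its table need reconciling.
- **The next visit in Appendix 3 could be the month-30 one**, since 8.4.1 and 9.5 call it a visit. But the schedule leaves both the visit row and the adverse-event row empty there, so the interview has no place in it.
- **No comparative safety endpoint is listed.** Objectives, endpoints and hypotheses concern radiographs and patient-reported outcomes, adverse events are defined by association with study intervention, and the safety set holds only exposed participants. This limits the consequence. What stands is the contrast within that set between those on MTX and those who have stopped, which an analysis by treatment received could bring out.

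**Conclusion.** The point holds as a modest, low-cost improvement. No event enquiry is scheduled at month 30 for any of the four groups, and active ascertainment between M12 and M30 has no common schedule. Capture is therefore likely to be denser in current MTX users, which sits badly with the commitments in 8.4.1 and 8.4.2 and could distort the safety analysis planned in 9.2.

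This rests on two assumptions: that outpatient contact is more frequent on MTX, as the intervals in 8.3 suggest, and that recurring contact raises the chance of an event being recorded.

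A reader might want to express this as an inflated risk ratio. With equal true risk p and detection probabilities d₁ on MTX and d₀ off it, the apparent ratio is p·d₁/(p·d₀) = d₁/d₀. It is simply the ratio of two detection rates, and the documents give neither, so no such figure is offered. Nor do the documents show that any comparison would necessarily overstate harm on MTX. It could, if one were made.

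**What to change.** 1. Mark adverse events in the M30 column of the Schedule of Activities for all four groups.
2. Add the same short AE/SAE item, with event dates, to the month-30 electronic questionnaire. Follow each positive answer with a telephone call and the record review that Appendix 3 already foresees.
3. State how events that began after M12 but before MERINO:2 consent are handled, because the item will elicit them and 8.4.1 does not cover them.
4. State that any between-group comparison of events uses those ascertained by this common route.
5. Reconcile the coverage of all participants in 8.3 with its treatment-based table, notes 9 and 10 of the schedule, and the next-visit wording in 10.3.1.

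The cost is one or two questionnaire items, a call for positive answers and some editing, with no extra visit. The main weakness is recall over up to 18 months. In an open-label study recall may itself differ by group, so the change makes the enquiry uniform but does not remove all detection bias.

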8.4.3. Follow-up of AEs and SAEs

After the initial AE/SAE report, the investigator is required to proactively follow each participant at subsequent visits/contacts. All SAEs and AEs of special interest (as defined in Section 8.4.6) will be followed until resolution, stabilization, or the event is otherwise explained. Further information on follow-up procedures is provided in Appendix 3.

8.4.4. Regulatory Reporting Requirements for SAEs

- Prompt notification by the investigator to the sponsor of an SAE is essential so that legal obligations and ethical responsibilities towards the safety of participants and the safety of a study intervention under clinical investigation are met.
- The sponsor has a legal responsibility to notify both the local regulatory authority and other regulatory agencies about the safety of a study intervention under clinical investigation. The sponsor will comply with country-specific regulatory requirements relating to safety reporting to the regulatory authority, institutional review boards (IRBs)/independent ethics committees (IECs), and investigators.
- An investigator who receives an investigator safety report describing an SAE or other specific safety information (eg, summary or listing of SAEs) from the sponsor will review and then file it along with the IB and will notify the IRB/IEC, if appropriate according to local requirements.
- Investigator safety reports must be prepared for suspected unexpected serious adverse reactions (SUSARs) according to local regulatory requirements and sponsor policy and forwarded to investigators as necessary.

8.4.5. Pregnancy

• A female/male participant must be instructed to immediately inform the investigator if she/his partner becomes pregnant during the study. For details on collection of pregnancy information, see Appendix 4.

- While pregnancy itself is not considered to be an AE or SAE, any pregnancy complication or elective termination of a pregnancy for medical reasons will be reported as an AE or SAE.
- Abnormal pregnancy outcomes (eg, spontaneous abortion, fetal death, stillbirth, congenital anomalies, ectopic pregnancy) are considered SAEs and will be reported as such.
- The participant/pregnant female partner will be followed to determine the outcome of the pregnancy. The investigator will collect follow-up information on the participant/pregnant female partner and the neonate and the information will be forwarded to the sponsor.
- Any poststudy pregnancy-related SAE considered reasonably related to the study intervention by the investigator will be reported to the sponsor as described in Section 8.4.4. While the investigator is not obligated to actively seek this information in former study participants/pregnant female partner, he or she may learn of an SAE through spontaneous reporting.
- A pregnant participant should be withdrawn from the study.

8.4.6. Adverse Events of Special Interest

A prolonged cough of more than 4 weeks duration is of special interest and should be followed up promptly with a CT of the lungs.

8.5. Pharmacokinetics

Pharmacokinetic parameters are not evaluated in this study.

8.6. Pharmacodynamics

Pharmacodynamic parameters are not evaluated in this study.

8.7. Genetics

Genetics are not evaluated in this study.

8.8. Biomarkers

Biomarkers are not evaluated in this study.

8.9. Immunogenicity Assessments

Antibodies are not evaluated in this study.

8.10. Medical Resource Utilization and Health Economics

Medical resource utilization and health economics parameters are not evaluated in this study.

9. Statistical Considerations

The analysis and reporting will be done on all data from all participants at the time the study ends. The statistical analysis plan will be finalized prior to database lock, and it will include a more technical and detailed description of the statistical analyses described in this section. This section is a summary of the planned statistical analyses of the most important endpoints including primary and secondary endpoints.

9.1. Statistical Hypotheses

The primary objective is to demonstrate that MTX is superior to treatment as usual in achieving slower radiographic progression at 30 months. Thus, the null hypothesis to be tested in relation to the primary estimand is as follows:

• Null hypothesis: MTX treatment for 30 months is not different from placebo (12 months) and subsequent treatment as usual (18 months) with respect to the progression of Verbruggen-Veys scoring system in participants with erosive hand OA.

VS.

• Alternative hypothesis: MTX treatment for 30 months is different from placebo (12 months) and subsequent treatment as usual (18 months) with respect to the progression of Verbruggen-Veys scoring system in participants with erosive hand OA.

Secondary outcomes (1):

- Null hypothesis: MTX treatment for 30 months is not different from placebo (12 months) and subsequent treatment as usual (18 months) with respect to the progression of KL scale or OARSI atlas in participants with erosive hand OA.
- Alternative hypothesis: MTX treatment for 30 months is different from placebo (12 months) and subsequent treatment as usual (18 months) with respect to the progression of KL scale or OARSI atlas in participants with erosive hand OA.

Secondary objective (2)

- Null hypothesis: MTX is not different from placebo/treatment as usual with respect to change from baseline to 12/30 months in OMERACT-OARSI responder criteria, AUSCAN or EQ-5D-5L.
- Alternative hypothesis: MTX is different from placebo/treatment as usual with respect to change from baseline to 12/30 months in OMERACT-OARSI responder criteria, AUSCAN or EQ-5D-5L.

Multiplicity control is not relevant for the study.

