The MERINO:2 is an extension of the MERINO trial (EudraCT number 2019-004641-33, Clincaltrials.gov number NCT04579848, REK ID 2020/187524, CTIS number 2023-510523-30-00), with an expanded observational period of 18 months after ending the MERINO trial (i.e. 30 months after staring MERINO). MERINO:2 is an investigator-initiated and open-label observational study. Participants are male and female adults with erosive hand osteoarthritis. Following the completion of the MERINO trial, participants either ended their treatment or were prescribed MTX open-label (oral or s.c. 5-25mg per week as well as folic acid 1mg daily).

Brief Summary:

The primary aim is to demonstrate the superiority of Methotrexate (MTX) over treatment as usual in slowing radiographic progression over 30 months in individuals with erosive hand osteoarthritis (OA).

OA is a leading cause of disability and affecting millions worldwide, with a significant impact on knee, hip, and hand joints. Despite its high prevalence and symptomatic burden, effective disease-modifying treatments remain elusive, with current options limited to pain management and joint replacement.

MTX, recognized for its disease-modifying effects in systemic inflammatory joint diseases, offers promising potential in OA treatment, with previous trials indicating its anti-inflammatory properties and potential for joint damage reduction. In the ongoing MERINO trial, 153 participants are randomly assigned to either MTX or a placebo. Following completion of the trial, several participants have expressed interest in MTX treatment, which is sometimes used off-label for erosive hand OA patients experiencing unmanageable pain and inflammation. As a result, some MERINO trial participants will receive MTX treatment.

In the MERINO:2 study, we will conduct a structured follow-up 18 months post-MERINO trial completion, incorporating hand radiographs and pain questionnaires. This endeavor will furnish invaluable insights into the long-term effects of MTX treatment in erosive hand OA, a gap in current knowledge, particularly regarding structural progression. This will provide valuable data on long-term effects of MTX treatment in erosive hand OA, which is not currently described in the literature, especially on structural progression.

Number of Participants:

We estimate 153 recruited participants from the MERINO trial as potential candidates for the MERINO:2 trial.

Study Arms and Duration:

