All participants recruited to the MERINO trial will be asked to provide conventional radiographs and electronic questionnaires 30 months after starting the MERINO trial. This results in four potential arms of the MERINO:2 trial, depending on the two former arms of the MERINO trial, each with a duration of 12+18=30 months:

- MTX \rightarrow MTX
- MTX \rightarrow Treatment as usual
- Placebo \rightarrow MTX
- Placebo \rightarrow Treatment as usual

Data Monitoring/Other Committee: No

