4.1. Overall Design

The MERINO:2 is an investigator-initiated and open label observational study with one-year parallel group treatment with MTX in male and female adults with erosive hand osteoarthritis.

Eligible participants are those recruited to the MERINO-trial (EudraCT number 2019-004641-33, Clincaltrials.gov number NCT04579848, REK ID 2020/187524, CTIS number 2023-510523-30-00).

After the MERINO trial, participants may either continue treatment as usual or be prescribed MTX open-label (oral or s.c. 5-25mg per week as well as folic acid 1mg daily).

Especially of interest is to compare those who first receive placebo and then treatment as usual throughout the MERINO and MERINO:2 trials with those receiving MTX throughout the whole period, as this comparison will reflect the effect of long-term treatment with MTX over 2,5 consecutive years. Further, the Placebo→MTX crossover group will complement the data from the MERINO trial on shorter MTX treatment.

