4.3. Justification for Dose

Being an open-label observational study, the doses and treatment length of MTX will vary depending on the physicians and participants preferences. At the one-year control, we will use self-reported doses and The Norwegian Prescription Database (Reseptregisteret) to calculate the doses during the follow-up year.

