6.3. Assignment to Study Intervention

The treating physician will decide, based on best clinical practice, if the patient should try MTX after the MERINO-trial. Central to this approach is the collaborative effort between the physician and participant, fostering an environment where patient perspectives are integral to treatment decisions. It will be emphasized by the physician prescribing MTX open-label that this is not evidence-based treatment until results of the MERINO-trial are published. We do, however, justify the continuation of MTX based on recent results from the METHODS trial (5). In the cases where the physician finds an indication for trying MTX after the MERINO trial, usual practice would be to try MTX for three months and then evaluate whether the patient should continue the treatment or not, based on synovitis scores and self-reported effects.

As described in section 5, this result in four groups in the MERINO:2 study, but since MTX treatment length and MTX doses could vary substantial in the observational time of the MERINO:2 study, we will adjust for this in the analyses.

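### The primary hypothesis names 30 months of MTX, but the groups carry no minimum exposure and the protocol does not place people who stop early

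*Protocol*

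**What the plan says.** Section 9.1 writes the exposure into the primary null hypothesis: "MTX treatment for 30 months is not different from placebo (12 months) and subsequent treatment as usual (18 months"). The same 30-month wording returns in the secondary hypothesis on KL and OARSI scores. Section 4.1 sets placebo followed by treatment as usual against "those receiving MTX throughout the whole period" and states that "this comparison will reflect the effect of long-term treatment with MTX over 2,5 consecutive years". The synopsis lists four arms, "each with a duration of 12+18=30 months".

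Entry to the arms is described differently. In the synopsis, after MERINO "participants either ended their treatment or were prescribed MTX open-label". Section 6.3 leaves the choice to the treating physician. Where MTX is thought worth trying, "usual practice would be to try MTX for three months and then evaluate whether the patient should continue the treatment or not", judged on synovitis scores and self-reported effect. The same section adds that "since MTX treatment length and MTX doses could vary substantial in the observational time of the MERINO:2 study, we will adjust for this". Section 4.3 says that "the doses and treatment length of MTX will vary depending on the physicians and participants preferences". Section 9.2 analyses efficacy by planned intervention, and under section 7.2 a person who stops for good is still invited to follow-up. No section gives a minimum time on MTX for any group.

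**The concern.** The 30 months is the length of follow-up. It is also the length of treatment only if MTX is taken without a break to month 30. Sections 9.1 and 4.1 use it as treatment length, while section 6.3 expects treatment length to differ within the groups. Length on MTX can differ only among people who took it, so section 6.3 implies that short-term users sit inside the → MTX groups.

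At stake is what the p-value at study end supports. A null result could be read as no effect of 30 months of MTX when an unknown share had much less. A positive result could be credited to a duration that the grouping does not guarantee. Restricting the group afterwards to people who stayed on MTX would instead favour those judged to be doing well on it.

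**Working it through.** **The plan's own figure.** 12 + 18 = 30 months (synopsis). The month-30 visit is at week 130 in the schedule of activities: 130 / 52 × 12 = 30.0. Section 4.1: 2.5 × 12 = 30. The figure reproduces as follow-up time.

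**One person's exposure.** Inputs: 12 months of MTX in MERINO (Table 2) and *s* months of open-label MTX afterwards. Total = 12 + *s*.

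| *s* (months) | Total | Share of 30 | Share of the 18 in MERINO:2 |
|---|---|---|---|
| 3 | 15 | 50% | 17% |
| 6 | 18 | 60% | 33% |
| 12 | 24 | 80% | 67% |
| 18 | 30 | 100% | 100% |

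The *s* = 3 row is the usual try period in section 6.3. Fifteen months is not a floor: section 5 invites everyone who entered MERINO, so 12 full months of MTX there is not assured.

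**Group mean.** The share *p* stopping at three months is not in the protocol. Taking it as an assumption, with everyone else continuing to month 30, the mean total is 30 − 15*p* and the mean within MERINO:2 is 18 − 15*p*.

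| Assumed *p* | Mean total (of 30) | Mean in MERINO:2 (of 18) |
|---|---|---|
| 20% | 27.0 | 15.0 |
| 30% | 25.5 | 13.5 |
| 50% | 22.5 | 10.5 |

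**Does adjustment for length recover the 30-month effect?** The protocol gives no form for the adjustment, so take the simplest: outcome = *a* + *b*·group + *c*·*L*, with *L* the months on MTX in MERINO:2. In placebo → treatment as usual, *L* = 0 by definition.

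- The coefficient *b* is then the group difference at *L* = 0, not at 18 months.
- The 30-month contrast would be *b* + 18*c*.
- With these two groups, *c* is estimated only from differences in length among MTX users. Those differences arise after baseline and depend on response, because continuation rests on synovitis and reported effect. Adding the placebo → MTX group brings in more data of the same kind.

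Neither *b* nor *b* + 18*c* is therefore a clean estimate of what section 9.1 names.

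**The case against.** The strongest reply is that section 4.1 already limits the comparison to "those receiving MTX throughout the whole period". Together with the 30 months in section 9.1 and the 18-month column heading in Table 2, this can be read as continuous users only. That stands as far as it goes. A reader might infer that a three-month stopper is definitely counted as MTX → MTX, but no sentence says so. Section 9.2 does not settle it either: MERINO:2 assigns nothing, and planned intervention may mean the MERINO arm. The continuous-user reading is not a way out, though. No group or analysis set applies it, and it selects on response.

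Three further points have weight. The three-month practice is worded for trying MTX, while section 6.3 speaks separately of continuing it, so how often it applies to people already treated for a year is uncertain. The protocol also recognises variable exposure, promises to adjust for it, and plans to collect dose and length by self-report and from the prescription database. Last, an exposure threshold could properly be left to the SAP, so its absence is no fault in itself. What remains is that the hypothesis is fixed in the protocol and does not agree with section 6.3; a SAP would have to choose between them.

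**Conclusion.** The conflict is real on either reading. If every prescribed user is included, the contrast carries a 30-month label that the grouping does not guarantee: a person who stops after the usual try has about half the stated exposure overall and about one sixth of the MERINO:2 period. If only continuous users are included, the MTX side is selected on response.

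The 15-month figure assumes a full year of MTX in MERINO and a stop at three months. The group means rest on assumed stopping shares. A reader might go further and conclude that many or most of the group had only half the exposure. The documents give no stopping rate and do not support that; at an assumed 20%, the mean is still 27.0 of 30 months (90%). The conclusion concerns what the result can be attributed to, not a known degree of dilution.

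**What to change.** Before database lock, reconcile sections 9.1 and 4.1 with sections 6.3 and 9.2:

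- State the primary contrast as MTX in MERINO with MTX prescribed after MERINO, within a stated window after month 12, versus placebo in MERINO with no MTX prescribed in that window, regardless of later stopping or starting. A window is needed because the protocol fixes no date for the decision.
- Do not use estimates adjusted for treatment length as primary.
- Report MTX months and dose in each group from the prescription database and self-report already planned in sections 4.3 and 6.5.
- Label any analysis of continuous 30-month users as supportive and subject to selection on response.

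The cost is rewording and one table from planned data. The claim about duration becomes weaker, and the question becomes one about a prescribing strategy. Confounding by indication remains, since treatment after MERINO is chosen and not randomised. No clinical rule on stopping or continuing MTX is proposed.
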